4.2. Number of cases, grouping and study centers

According to the China National Stroke Registry (CNSR), 39.59% of patients with NIHSS Page 7 of 76

score of 4–22 at admission had mRS \leq 1 at 3 months. Assuming a 40% proportion of patients with mRS \leq 1 at 90 days in the control group and a 47% proportion in the treatment group, with an equal ratio design, and utilizing PASS 2008 to calculate the required sample size, with α = 0.05 (two-sided test) and β = 0.2 (test power 80%), the calculated sample size for both the treatment and control groups is 787 cases. To account for potential dropouts in clinical studies, an additional 20% of the sample size is added. Therefore, a total of 1,968 patients are planned to be included in this study.

Patients will be allocated in a 1:1 ratio to the treatment group and the control group, and the study is planned to be conducted at 50 centers nationwide.

5. Study Population

Patients entering the study must meet all the inclusion criteria listed below and must not meet any of the exclusion criteria. In addition to the criteria listed below, any medical conditions or use of prohibited medications during the standard treatment that are considered contraindications will also be grounds for excluding patients from the study.

5.1. Inclusion criteria

- 1. Ischemic stroke within 72 h after onset, confirmed by MRI or CT;
- 2. Age 35–75 years, inclusive;
- 3. Patients with the first attack or patients with stroke history (modified Rankin Scale score 0-1);
- 4. Clear signs of localization of nervous system, NIHSS score 4 to 22;
- 5. Patient or proxy has signed *Informed Consent Form*.

5.2. Exclusion criteria

- 1. Hemorrhage diseases according to head CT, such as hemorrhagic stroke, epidural hematoma, intracranial hematoma, intraventricular hemorrhage, subarachnoid hemorrhage and hemorrhage after cerebral infarction;
- 2. Transient ischemic attack (TIA);
- 3. Severe disturbance of consciousness: 1a of NIHSS score >1 point; Difficulty in swallowing, unable to take oral capsules; any of 5a, 5b, 6a, 6b of NIHSS score >2 point.

- 4. Convinced of stroke caused by brain tumor, brain trauma, hemopathy, etc.;
- 5. Hemorrhagic tendency patients;
- 6. Patients with endovascular treatment after the onset of stroke;
- 7. Patients with dementia, severe Parkinson's disease, mental disorders, limb dysfunction caused by other diseases or other conditions that may affect the efficacy determination;
- 8. Uncontrolled hypertension (≥200 mmHg systolic or ≥110 mmHg diastolic) or hypotension (≤90 mmHg systolic or ≤60 mmHg diastolic); severe hyperglycemia (blood glucose ≥400 mg/dL)
 - (22.2 mol/L) or hypoglycemia (blood glucose ≤50 mg/dL) (2.8 mol/L);
- 9. Severe hepatic insufficiency defined as transaminase values >2x upper limit of normal; severe renal insufficiency defined as values serum creatinine >1.5x upper limit of normal; cardiac dysfunction or other serious systemic disease with life expectancy ≤3 months;
- 10. Patients with concurrent malignancy or ongoing anti-tumor therapy;
- 11. Patients with history of being allergic to study drug and control drug;
- 12. Pregnancy, breastfeeding or potential pregnancy;
- 13. Within three months or currently participating in another investigational study;
- 14. Any other condition that in the opinion of the investigator should preclude study participation.

5.3. Dropout (withdrawal) criteria

Any subjects who have signed the *Informed Consent Form* and been screened for eligibility, regardless of when or why they withdraw, will be considered dropouts if they do not complete the protocol-defined procedures.

Patients have the right to withdraw from the study at any time and for any reason. The investigators also have the right to withdraw a patient from the study if the patient experiences illness, adverse events, protocol violations, or for management reasons or any other reason. Efforts should be made to minimize unnecessary patient withdrawals, and proactive measures should be taken to complete the final assessment whenever possible, to facilitate the analysis of their efficacy and safety. However, when a patient decides to withdraw, the investigators should contact the patient or their responsible family member through telephone or in-person visits to confirm the reasons for withdrawal. Investigators should retrieve any remaining study

drug, complete the final assessment, strive to finalize case reports, explain the reasons for withdrawal, and conduct follow-up on endpoint events for withdrawn patients whenever possible. If a patient withdraws from the study due to adverse events, the primary event should be documented in the study medical records.

Common reasons for dropouts: Adverse events, lack of efficacy, patients undergoing endovascular therapy during the follow-up period, protocol violations (including poor compliance), loss to follow-up (including voluntary withdrawal by patients), discontinuation by the sponsor, etc.

5.4. Termination criteria

- 1) Occurrence of allergic reactions clearly related to the study drug;
- 2) Occurrence of adverse symptoms, signs, or abnormal test results clearly related to the study drug, as judged by the investigator, necessitating the termination of the study;
- 3) Occurrence of pregnancy in females during the study period;
- 4) Termination of continued participation in the study at the patient's request;
- 5) Undergoing endovascular therapy during the study period;
- 6) The occurrence of vascular events will be evaluated on a case-by-case basis: In the event of hemorrhagic stroke, the study drug should be discontinued, the study terminated, and the details documented in the relevant sections of the study medical records. If a TIA/ischemic stroke/myocardial infarction occurs, the subject does not need to discontinue the study drug or withdraw from the study unless the use of concomitant medication contraindicated in this study is necessary.

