6.1.6.3 Handling plan for patients permanently discontinuing the drug

The follow-up of patients should adhere to the procedures specified in the study protocol, continuing until the scheduled completion date of the study or until the patient recovers to normal or stable condition from adverse events (whichever is longer).

The investigator should record all confirmed withdrawals from the study on the corresponding pages of the CRF.

Patients who discontinue the study drug before the last follow-up should complete the endpoint follow-up at 3 months.

For patients lost to follow-up, relevant information should be documented up to the last follow-up in their CRFs. The investigator should make every effort to contact each patient, ascertain the reason for loss to follow-up, and assess their health status.

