8.6 Follow-up for potential events

If a patient experiences potential clinical neurological events, including clinical symptoms due to ischemia or new transient or persistent neurological symptoms, each center is required to generate a determination document within 72 hours. The content should include:

- Conduct neurological examination (mRS, NIHSS, BI)
- Perform physical examination, record body weights and vital signs
- Collect information on concomitant medications and adverse events since the last Page 18 of 76

follow-up.

 Patients participating in the radiology subgroup should undergo MRI sequence examinations, and their imaging results should be transmitted to the central imaging reading room.

If a patient experiences a new potential cardiovascular event, a cardiac assessment, including an ECG, will be conducted based on clinical need. Any information supporting a potential myocardial infarction will be collected in the determination document and communicated to the CRA within 72 hours.

9 Efficacy and Safety Determination Criteria

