12.1 Analysis population

The study population is divided into the following categories:

- Full Analysis Set (FAS): The set of subjects according to the Intention To Treat (ITT) principle. It refers to the dataset composed of all subjects who participated in the randomization process and underwent baseline assessments. For subjects for whom complete efficacy assessments are not observed, data truncation will be carried out following the Last Observation Carried Forward (LOCF) principle.
- Per-Protocol Set (PPS): It refers to the collection of cases that meet the inclusion criteria, do not meet the exclusion criteria, and complete the treatment regimen. This includes cases that adhere to the study protocol, exhibit good compliance, and complete the specified CRF entries for analysis (PP analysis).
- Safety Set (SS): It refers to the set of all randomized subjects who received the study drug and had at least one safety assessment after baseline.

The efficacy analysis will be conducted based on the FAS and the PPS. The analysis of all baseline demographic data will be conducted based on the FAS, and safety assessment will be performed on the SS.

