12.2 Statistical analysis method

- All statistical tests will be two-sided, and a *P*-value ≤0.05 (two-sided) will be considered statistically significant for the tested differences. (Unless specifically stated otherwise)
- Descriptive analysis: For count data, describe with proportions. For measurement data,

- describe with mean, standard deviation, maximum, and minimum values. For non-normally distributed data, describe with median, 25th percentile, and 75th percentile.
- The comparison of general conditions between the two groups will be analyzed using appropriate methods based on the type of indicator. Inter-group comparisons of quantitative data will be performed using paired t-tests or Wilcoxon rank-sum tests. For categorical data, the chi-square test or exact probability method will be employed. For ordinal data, Wilcoxon rank-sum tests or CMH tests will be used.

12.2.1. Enrollment and study completion:

Summarize the number of enrollments and completions for each center and provide a list of dropouts. Different dataset sizes for each group, distribution of cases in each center, comparison of overall dropout rates, and a detailed list of reasons for termination. Describe the demographic characteristics of patients (age, height, weight, vital signs, etc.), medical history, and medication history. Compare age, height, and weight between the two groups to assess their comparability.

12.2.2. Compliance analysis:

- Medication compliance analysis: Compare whether patients in the two groups use the study drug on time and in the correct dosage, and whether they refrain from using prohibited drugs and foods according to the protocol.
- Concomitant medication analysis: Tally the number of patients in each group using concomitant medications and provide a detailed list.

12.2.3. Efficacy evaluation:

- Baseline: Describe the baseline characteristics of each efficacy indicator. Refer to general methods for inter-group comparisons.
- Primary efficacy endpoints:

Conduct both PP and FAS analyses concurrently. The primary time point for evaluating the proportion of patients with improved modified Rankin (mRS) scores ≤ 1 in terms of activities of daily living is at Day 90 (for the PP population) or at the time of premature discontinuation (for the FAS population). The primary indicator will be compared between the two groups using the CMH- χ^2 analysis method, controlling for center effects.

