4.5.4 Standards for suspending the study

- 1. Having allergic reaction clearly associated with study drugs;
- 2. Having adverse symptoms and signs definitely associated with study drugs, abnormal findings, or conditions in need of ending the study after judgment of researchers, which are clearly related to the medicine under study;
 - 3. Female subjects get pregnant during the study;
 - 4. The patients ask to end further study;
 - 5. Take endovascular treatment during study period;
- 6. If there is occurrence of vascular events, it should be determined as appropriate: Discontinue study drug and terminate study, if the patient has hemorrhagic stroke, and the related condition should be recorded in appropriate part of medical records. If there is occurrence of TIA/ ischemic stroke/ myocardial infarction, the subjects do not need to discontinue taking study drug or withdraw from the study, only if concomitant drugs contraindicated by the study need to be taken.

5. Evaluation index

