6.1.1 Full analysis set (FAS)

Full analysis set (FAS) or modified intention-to-treat (ITT): Set of all the patients who underwent randomization, given any treatment, and underwent any posttreatment assessment. When main indexes of curative effect are missing, the set should be supplemented with last observation carried forward (LOCF) on the basis of intention to treat (ITT). Comparability analysis and the missing value of secondary effect indexes don't need data-carry-forward. Take analysis on actual data in FAS.

FAS population is the main population for curative evaluation in this study.

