6.2.4 Efficiency evaluation

Baseline efficiency: Describe the baseline of each curative index, and comparison between groups should be made in accordance with general condition. Modified Rankin (mRS) score is regarded as ranked data, and should be compared with Wilcoxon rank sum test. NIHSS score should be regarded as quantitative data and ranked data (4-7 points, 8-14 points and 15-22 points) for description and comparison; BI score as quantitative data and enumeration data (<85 points, ≥85 points) for description and comparison.

Primary efficiency indexes:

PP analysis and FAS analysis should be performed at the same time; evaluation on patients with modified Rankin (mRS) score≤1 should be mainly conducted ontaken at day 90 day (PP set) and the time for suspending and drop-out (FAS set). Primary indexes should be compared between the two groups with CMH-γ2 method for controlling central effect.

Superiority test is adopted for primary indexes, and the hypotheses under test are as follows:

$$H_0$$
: $\pi_{\text{treatment group}} - \pi_{\text{control group}} \le 0$

$$H_1: \pi_{\text{treatment group}} - \pi_{\text{control group}} > 0$$

$$\alpha = 0.025_{\text{(one-sided)}}$$

The treatment group is superior to control group, if H0 is rejected under α level, or lower limit of 95% Cl for difference of retention rate between the two groups is higher than 0. Take sensitivity analysis on primary efficiency indexes with modified Rankin (mRS) score≤2 points as the limit.

Other secondary indexes can be statistically analyzed in accordance with methods for primary indexes.

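### Haemorrhagic stroke ends study participation as well as study drug, and the FAS timing rule then allows a score earlier than Day 90 to stand as the primary mRS

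*Combined protocol and SAP*

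**What the plan says.** **Termination.** Protocol 5.4 item 6: "In the event of hemorrhagic stroke, the study drug should be discontinued, the study terminated, and the details documented". SAP 4.5.4 item 6: "Discontinue study drug and terminate study, if the patient has hemorrhagic stroke". In both documents the next sentence deals with TIA, ischaemic stroke and myocardial infarction. It says these patients need neither stop the drug nor withdraw, unless a contraindicated medication is required.

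**Follow-up after stopping drug.** Protocol 6.1.6 asks that patients remain in the study for as long as is feasible, whatever the circumstances. Protocol 6.1.6.3 adds: "Patients who discontinue the study drug before the last follow-up should complete the endpoint follow-up at 3 months". At withdrawal, protocol 5.3 asks for a final assessment and, where possible, follow-up of endpoint events. SAP 4.5.3 asks for a final assessment and follow-up on the endpoint. Neither names a Day-90 mRS.

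**Timing of the primary analysis.** Protocol 12.2.3 evaluates mRS ≤1 "at Day 90 (for the PP population) or at the time of premature discontinuation (for the FAS population"). SAP 6.2.4 has Day 90 for the PP set and "the time for suspending and drop-out (FAS set"). SAP 6.1.1 makes the FAS the main efficacy population.

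**Missing data.** For subjects without complete efficacy assessments, protocol 12.1 says "data truncation will be carried out following the Last Observation Carried Forward (LOCF) principle". SAP 6.1.1 says "When main indexes of curative effect are missing, the set should be supplemented with last observation carried forward (LOCF").

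**The concern.** The primary endpoint is mRS ≤1 at 90 days after randomization (synopsis; protocol 9.1.1). Two pieces of text can put an earlier score in its place for the same patients. The termination rule gives a site grounds to close out a patient after a bleed, so Day 90 may never be collected. The FAS timing rule then names the moment of discontinuation as the evaluation point. Recovery, worsening or death between that moment and Day 90 would not reach the primary analysis.

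Haemorrhagic stroke is an outcome the drug itself might affect, so terminations could differ between arms. In that case the loss would not cancel out.

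**Working it through.** **Does item 6 end participation, or only drug?** Item 6 lists two acts, stopping drug and terminating the study. The following sentence exempts other vascular events from both stopping drug and withdrawing. Whole-trial stopping has its own section, protocol 5.5. So termination here means that the patient leaves the study. That conflicts with 6.1.6 and 6.1.6.3, and item 6 does not refer to either. The SAP has no section matching 6.1.6.3; SAP 4.5.3 comes nearest.

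**What would be analysed?** Protocol 8.6 requires an assessment at new neurological symptoms ("Conduct neurological examination (mRS, NIHSS, BI")), documented within 72 hours, and 5.3 asks for a final assessment. The carried score is therefore probably post-bleed, but still earlier than Day 90. The Appendix 2 scale runs from 0 to 5 with no level for death, so carrying forward assigns a living score to a patient who dies. This alters the primary endpoint only if that last score was 0 or 1. Protocol 11.2 and SAP 4.3.2 class emergency-unblinded patients as drop-outs, so the FAS timing wording reaches them too.

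**The plan's own figures.** Inputs from protocol 4.2 and SAP 4.4: 40% against 47%, two-sided α 0.05, power 80%.
- n = [1.960√(2p̄q̄) + 0.842√(p₁q₁ + p₂q₂)]² / Δ², with p̄ = 0.435.
- n = [1.960 × 0.7011 + 0.842 × 0.6994]² / 0.07² = 787 per group after rounding up.
- 787 / 0.80 = 983.75, so 984 per group and 1,968 in total. The stated figures reproduce.
- Power at 984 per arm = Φ{[Δ√n − 1.960√(2p̄q̄)] / √(p₁q₁ + p₂q₂)} = Φ{[0.07 × 31.369 − 1.374] / 0.6994} = Φ(1.175) = 88.0%.

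**Size, on assumed rates.** The documents give no on-study termination rate. I assume f = 0.5 to 5% for all terminations. The nearest figure in the documents is symptomatic haemorrhagic transformation of 1.5 to 5% (Appendix 7), which concerns ischaemic stroke in general and lies inside this range.
- Patients affected: 984 × 0.005 = 4.9 to 984 × 0.05 = 49.2 per arm, or about 10 to 98 in total.
- Equal rates, every terminated patient counted as mRS >1 (both rates multiplied by 1 − f):
  - f = 0.5%: 46.77% against 39.80%, difference 6.965 points, power 87.7%.
  - f = 5%: 44.65% against 38.00%, difference 6.65 points, power 85.0%.
- Unequal rates: shift = gap in termination × share whose carried score falls on the wrong side of mRS 1. I assume a gap of 1 to 2 points (about 10 to 20 patients) and a share of 10 to 40%; 40% is the planned control success rate. The shift runs from 1 × 0.10 = 0.1 to 2 × 0.40 = 0.8 points.
- Example: 3% terminated on drug and 2% on control, 40% of them missed recoveries. 47 − 3 × 0.40 = 45.8%; 40 − 2 × 0.40 = 39.2%; difference 6.6 points, power 84.2%.
- A shift above 1 point needs a wider gap: 3% on control against 6% on drug at a 40% share gives 3 × 0.40 = 1.2 points.

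If carried scores miss recoveries, the arm with more terminations is penalised. If they hide worsening or death, it is flattered.

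**The case against.** The best defence is that follow-up is already required. A patient under item 6 has stopped drug, and 6.1.6.3 makes no exception for haemorrhagic stroke. Protocol 6.1.6 asks for continued participation in any circumstance, SAP 4.5.3 asks for follow-up on the endpoint, and item 6 opens by saying that vascular events are judged case by case. On this view there is one loose phrase and a missing cross-reference. That narrows the point but does not remove it: a site reading 5.4 alone is told to terminate, and SAP 4.5.3 does not say that the Day-90 mRS must be obtained.

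A reader might infer that the FAS rule discards a Day-90 score that was collected. The documents do not support this. Read literally, the rule would give the FAS no Day-90 evaluation even for completers, which cannot be meant. LOCF applies only where assessments are not observed or are missing (protocol 12.1, SAP 6.1.1), and SAP Table 7.3.2.1 reports mRS at 90 days in its FAS columns. The earlier score is more naturally a fallback. What stands is that 12.2.3 and SAP 6.2.4 do not say so.

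A reader might also infer that bleeds are hidden from view. They are not. A favourable pre-bleed score is carried only if both the 8.6 and the 5.3 assessments are missed. Adverse events are followed to resolution or stability under 6.1.6.3, 10.5 and 10.6.2.

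Finally, the effect is small and power stays above the planned 80% in each power calculation above. That stands.

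**Conclusion.** The conflict between 5.4 item 6 (with SAP 4.5.4 item 6) and 6.1.6/6.1.6.3 is real, and the FAS timing wording permits an early score in place of Day 90. It should be corrected, but it does not threaten the trial.

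On a termination gap of 1 to 2 points and 10 to 40% misclassified, the effect is 0.1 to 0.8 points on the planned 7, direction unknown. With equal termination rates up to 5%, power falls from 88.0% to no lower than 85.0%. These powers assume no other losses from the 984 per arm, and every termination and misclassification rate is an assumption.

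The firm case is haemorrhagic stroke. One might extend it to items 1 to 3 and 5 of 5.4, but the support is weaker. Item 2 rests on investigator judgement. Protocol 6.2.1 ends only study treatment for intolerable drug-related events. Protocol 6.1.6.2 lists pregnancy as a reason to stop drug, although 6.1.6 says it ends study participation.

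**What to change.** 1. Amend protocol 5.4 item 6 and SAP 4.5.4 item 6 so that haemorrhagic stroke ends study drug only. Day-90 mRS and vital status are then collected under 6.1.6.3 unless consent is withdrawn. For consistency, word the other non-consent items (1 to 3 and 5) and the pregnancy sentence in 6.1.6 the same way.
2. Amend protocol 12.2.3 and SAP 6.2.4 so that the FAS primary endpoint is the Day-90 mRS regardless of drug discontinuation or emergency unblinding. Impute only when Day 90 is truly missing, and count death before Day 90 as mRS >1.

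The drug-stopping rules and the sample size stay as they are. No visit is added, because 6.1.6.3 already requires the 3-month follow-up. Sites keep contact with a few patients they might otherwise close out: at the assumed 0.5 to 5%, 9.8/50 = 0.2 to 98.4/50 = 2.0 per centre over 50 centres. The FAS will include outcomes after drug is stopped, which is in line with the ITT principle stated in protocol 12.1.

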5.5. Criteria for comprehensive study discontinuance

- 1) During the study, the entire multi-center study may be fully suspended for the following reasons:
- ➤ The investigator discovers serious safety issues;
- The efficacy is too poor, and there is no need to continue the study;
- > Significant error in the protocol is found;
- > The sponsor decides to discontinue the study due to financial or managerial reasons;
- The study may be terminated midway in its entirety if the administrative regulatory

authority revokes the study.

The comprehensive discontinuance of the study can be either temporary or permanent. When

the study is discontinued, all study records should be retained for future reference.

6. **Treatment**

